 - A physician in [name] group will approach subjects who meet criteria for protocol 03-M-0093 and give them information about the study so that they may decide whether or not to participate.
 - Study information will also be distributed to local chapters of the Anxiety Disorders Association of America, Freedom from Fear, and the National Alliance for the Mentally Ill. All such advertisements have been submitted to the IRB by [name] and recently received IRB approval. Any new advertisements or changes to existing advertisements will be submitted to the IRB for approval prior to publication.
- NIH Employees, staff and family members will not be directly recruited by or through their supervisors or coworkers to participate in this study.

c. Screening

- Upon arrival for their face to face screening visit, participants will have the opportunity to fully review the 0093 protocol consent form and to ask questions. If they express interest in participating in the study, they will then be screened under the MAP Screening Protocol 01-M-0254 with the following measures to evaluate if they are indeed eligible for the study:

- Pregnancy test (urine test) for women of child bearing age
- Urine drug screen (amphetamines, benzodiazepines, cocaine/metabolites, opiates, morphine, codeine, THC)
- Wechsler Abbreviated Scale of Intelligence (WASI) (Weschler, 1999)
- Subject demographic information
- Vital signs (sitting blood pressure and pulse), height, weight
- Medical history and physical examination
- Structured Clinical Interview for DSM-IV (patients only)
- Structured Clinical Interview for DSM-IV-TR non-patients edition (non-patients only)
- Concomitant medication and pharmacotherapy history
- Inclusion/exclusion criteria

• Following the medical and psychiatric screening assessment under protocol 01-M-0254, English-speaking participants will be asked to fill out the following questionnaires:

- State-Trait Anxiety Inventory (STAI) (Spielberger, 1983)
- NEO-Personality Inventory (Costa & McCrae, 1992)
- Anxiety Sensitivity Index (Peterson & Reiss, 1992)
- Beck Anxiety Inventory (Beck & Steer, 1987)
- Beck Depression Inventory (BDI) (Beck & Steer, 1987)
- Fear Questionnaire (Marks & Mathews, 1979)
- Penn State Worry Questionnaire (Meyer, Miller, Metzger, & Borkovec, 1990)
- Positive and Negative Affectivity Scale PANAS (Watson, Clark, & Tellegen, 1988)

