Adverse events will be rated weekly. The primary efficacy measure will be the Clinical Global Impressions Scale (CGI) Improvement rating (Guy, 1976). The CGI is a well-documented outcome measure in studies investigating the efficacy of treatments for psychiatric disorders including social anxiety disorder (Liebowitz, et al., 1992), and panic disorder (Barlow, Gorman, Shear, & Woods, 2000). A second aspect of the CGI, the CGI Severity index, will also be administered. Clinician ratings of anxiety symptoms will be completed weekly. Anxiety symptoms will be rated with the Hamilton Rating Scale for Anxiety [HAM-A] (Hamilton, 1959).

Research Questionnaires used in each study: In addition to using the trait portion of the STAI to classify healthy controls as high or low in trait anxiety, the state portion of the STAI will be administered prior to every experimental task (i.e., test of orienting response to innocuous stimuli, dot probe, verbal threat, aversive conditioning, eyeblink conditioning) to assess subjective measures of fear and anxiety that may influence outcome measures from experimental tasks. The remaining research measures (NEO, BDI, BAI, cognitive tests, etc.) are given for exploratory purposes.

For the purposes of screening, we use a standard set of questionnaires to assess mood and anxiety for subjects including SCID, BDI-II, IDSR, HAM-D, HAM-A, and MADRS.

The non-analogue measures from these reports may be completed by the participant on the Clinical Trial Survey System (CTSS) online system. AIs may then collect data from the Clinical Trials Database (CTDB) for the purposes of this study. Participants may enter their responses while at NIH using a wireless-device interface to access the NIH-intranet secure CTDB. There are no potentially actionable questions to be used by this system and thus the answers will not require real-time monitoring.

e. End of Participation

- Participation in the studies is expected to be completed within six months, though precise timing depends on the needs of the patients. Subjects will be terminated from the protocol when they request to discontinue participation. Moreover, subjects requiring clinical care after the completion of treatment at NIH will transition to community-based clinicians. Clinical care will be provided in the community, outside of the current protocol.

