8. SUBJECT SAFETY MONITORING

- Subject monitoring will be conducted by the Principal investigator, [name], Ph.D.
- All patients will be monitored at each visit for their participation for signs of discomfort or desire to discontinue the protocol. Specifically, they are in constant view of the research staff during the experiment. They are instructed to wave at the (non-recording) camera or else to call the researcher if they wish to stop the experiment. The researcher is within earshot of the participant at all times. The participants will also be explicitly told during the consenting procedure as well as after the sample shock procedure that it is their right to discontinue the study at any time.
- **Criteria for Withdrawal:** If a patient experiences clinically significant worsening, displays any suicidal ideation or active plans of suicide, reports adverse reactions to the experiment at any point during the study, appears to be in distress at any point during the procedures, or demonstrates adverse responses by way of the post-experimental assessment of adverse events, the patient will meet with [name] or [name], or their clinical staff, who will assess the patient's suitability for continuation in the study and will administer appropriate psychiatric treatment. If the psychiatrist determines that continuation is clinically counter-indicated, the patient will be removed from the protocol but will receive treatment at the NIH under the care of [name] or [name] until appropriate, long-term psychiatric care is arranged. The reasons for patients' discontinuation from the study will be logged and changes to procedures necessary to prevent future adverse reactions will be made.
- **Role of Medical Doctors:** The medical advisory investigator for this study, [name], will serve as the primary treating psychiatrist for anxiety patients enrolled in this protocol. Dr.

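### The online questionnaires are exempted in blanket terms from real-time review as containing nothing actionable, although the measures referred to include depression self-report and other sections make suicidal ideation and worsening triggers for clinical review

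*Combined protocol and SAP*

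**What the plan says.** Section 4.d (Assessments) names the BDI as a research measure: "The remaining research measures (NEO, BDI, BAI, cognitive tests, etc.) are given for exploratory purposes". For screening it names a standard set used to "assess mood and anxiety for subjects including SCID, BDI-II, IDSR, HAM-D, HAM-A, and MADRS". The next paragraph opens the online route: "The non-analogue measures from these reports may be completed by the participant on the Clinical Trial Survey System (CTSS) online system". It ends with the exemption: "There are no potentially actionable questions to be used by this system and thus the answers will not require real-time monitoring".

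Section 4.c (Screening) lists the BDI among the questionnaires that participants fill out themselves.

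Section 8 (Criteria for Withdrawal) gives several triggers for a meeting with the responsible psychiatrists or their clinical staff, who assess whether the patient should continue. One begins "If a patient experiences clinically significant worsening"; another applies if the patient "displays any suicidal ideation or active plans of suicide". Section 4.e (End of Participation) separately commits to review of any symptom worsening by a panel of clinicians. Section 20.a (Confidentiality) says that all data are reviewed as they are collected.

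**The concern.** The sentence in section 4.d goes beyond leaving a detail out. It is a positive statement that nothing in the online answers could call for action, and it gives that as the reason for not monitoring them in real time. Staff who follow it have a stated reason not to look at a depression self-report when it comes in.

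The protocol enrols patients with major depression and bipolar depression and exposes participants to shock and social stressors. Section 7.g accepts that patients who are not on psychotropic medication may worsen, and offers symptom monitoring by medical staff as the safeguard. A depression self-report is one of the few places where a participant puts symptom information in writing. If it is declared non-actionable in one section while its subject matter triggers review in two others, staff cannot tell which instruction governs. The issue is participant safety; no analysis, power figure or sample size depends on it.

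**Working it through.** No arithmetic applies. The check sets the relevant sections side by side.

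1. **Which measures does the exemption cover?** Section 4.d refers back to the reports just listed, limited to the non-analogue ones. That term is not defined in the documents, and no scale is excluded by name. The measures named just before are the BDI (research) and BDI-II, IDSR, HAM-D, HAM-A and MADRS (screening), along with others.

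2. **Which of these does the participant complete?** Section 4.c settles it for the BDI. Section 4.d describes the HAM-A as a clinician rating, so it should not be counted. The documents do not say how the other depression scales are administered. At least one depression self-report therefore falls within the plain wording.

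3. **Is that content actionable under the protocol's own rules?** Section 8 makes any suicidal ideation, or worsening that is clinically significant, a reason for a clinical meeting. Section 4.e has a lower bar: any worsening goes to the panel. A depression self-report bears on both. Calling the BDI exploratory describes its place in the analysis, not its relevance to safety.

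4. **Does another section supply the missing review?**
   - Section 4.c and section 7.f: patients are assessed at the end of each visit, but for adverse reactions to the experimental procedures. Neither section mentions reading questionnaire answers.
   - Section 8, schedule of clinical assessments: patients have an initial psychiatric evaluation and SCID, a symptom-severity rating on arrival at each of the three sessions, and an end-of-session assessment. None is said to draw on online answers, and no separate suicidality assessment is listed.
   - Section 4.c, order of events: the questionnaires are filled out after the medical and psychiatric screening assessment, so that assessment cannot be assumed to have used the answers.
   - Section 4.d: participants may enter answers on site, and investigators may retrieve them. Both are optional, and no time is set.
   - Section 15: the investigator reports to the independent monitor annually, which is not a timely route for an individual answer.
   - Section 20.a: the data-review statement names no reviewer, timing or safety action. If it is read as a safety rule, it contradicts section 4.d.

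5. **Healthy volunteers.** The schedule in section 8 covers patients only. Healthy volunteers are watched by camera and audio during procedures, and procedures stop on request or on signs of distress. Neither brings a questionnaire answer to a clinician.

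**Result.** The exemption in section 4.d is not reconciled with sections 4.e, 8 and 20.a, and an online answer has no stated timely safety review or route to the clinicians named in sections 4.e and 8.

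**The case against.** The strongest reply is that patients are well covered in person. A clinician rates their symptoms on arrival, they are assessed before leaving, worsening goes to a panel, and psychiatric contact is available around the clock. Section 4.e says that all subjects are seen regularly by a trained clinician, and section 20.a says data are reviewed as they arrive. Screening runs under a separate protocol that is not available here. The undefined term may also have been meant to confine the online system to harmless forms.

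Much of this stands, and it limits the point. A reader might infer that a disclosed signal would go unread, or that the withdrawal criterion works only if the patient repeats the information aloud. The documents do not support either inference: lack of real-time monitoring is not lack of review, and the in-person assessments are independent routes to the same signal.

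A reader might also infer that the forms ask directly about suicidal thoughts. No questionnaire item is reproduced, so this must be checked against the forms in use. Nor can a rising depression score be assumed. The BDI is placed at screening, and only the state anxiety inventory is said to precede every task. Section 4.d does head these measures as used in each study, and section 10 allows participation in more than one sub-study, so repeat scores are possible, but none is scheduled.

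The reply does not remove the conflict. If the online set was meant to contain only harmless forms, the text does not say which they are, and the named measures point the other way. None of the safeguards is said to include reading the online answers.

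**Conclusion.** The point holds as an internal contradiction with a safety consequence. Section 4.d declares the online answers non-actionable and exempts them from real-time monitoring, while sections 4.e and 8 make the subject matter of a depression self-report grounds for clinical review and section 20.a promises review of all data. What is missing is a stated reader, a stated time and a stated route for an online answer.

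Its size cannot be expressed as a count. The accrual ceilings are 608 patients and 663 healthy volunteers, but online entry is optional, the forms entered online are not listed, and the documents give no rate at which answers would raise concern. For patients the practical gap is narrowed by the assessments at each visit. It is widest for healthy volunteers, who are not in the assessment schedule.

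The conclusion assumes only that the BDI, which participants fill out, is not excluded from the online set; the text does not exclude it. It does not depend on any particular questionnaire item.

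**What to change.** - Delete the blanket statement in section 4.d that the system contains no potentially actionable questions, or limit it to named forms for which it has been checked and is true.
- Define the non-analogue measures by listing every form that may be entered online, separately for patients and healthy volunteers.
- Check the forms in use for items that bear on the triggers in sections 4.e and 8.
- Reconcile section 4.d with sections 4.e, 8 and 20.a on who reviews online answers, when, and how an answer of concern reaches the responsible clinicians, including for healthy volunteers.

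The timing of the review and the clinical threshold for action are for the sponsor to set. The cost is a short amendment and a few minutes of form review. No change to design, sample size or analysis follows.

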5. STORAGE OF DATA AND SAMPLES

We collect up to 10 saliva samples for each research participant. Saliva samples are stored in Building 49, Rm #B1B56. Saliva samples are discarded once cortisol levels are extracted.

6. ADDITIONAL CONSIDERATIONS

a. Research with investigational drugs or devices

Acoustic startle and shock device used in this protocol are considered non-significant risk (NSR) devices and will only be used within published guidelines.

Auditory startle does not meet criteria for a Significant Risk device as outlined Under 21 CFR 812.3(m), as an investigational device that:

1. Is intended as an implant and presents a potential for serious risk to the health, safety, or welfare of a subject

Response: Auditory startle is not an implantable device.

2. Is purported or represented to be for a use in supporting or sustaining human life and presents a potential for serious risk to the health, safety, or welfare of a subject

Response: Auditory startle is not for use in supporting or sustaining human life. It does not present a potential for serious risk to the health, safety, or welfare of participants when used as described in this protocol.

3. Is for a use of substantial importance in diagnosing, curing, mitigating, or treating disease, or otherwise preventing impairment of human health and presents a potential for serious risk to the health, safety, or welfare of a subject

Response: Auditory startle, as used under this protocol is not of substantial importance in diagnosing, curing, mitigating, or treating disease, or otherwise preventing impairment of human health and does not present a potential for serious risk to the health, safety or welfare of a subject.

4. Otherwise presents a potential for serious risk to the health, safety or welfare of a subject

Response: Auditory startle has been in use numerous for decades and have been cleared by the FDA. Safety guidelines have been developed and updated allowing its dissemination to a wide range of clinical and non-clinical settings. The FDA has generally waived pre-IDE inquiries for auditory startle studies on an NSR device basis. Hence, the CNS IRB, like most US IRBs, has accepted NSR designation for auditory startle within these limitations.

The shock device (electrical stimulator) does not meet criteria for a Significant Risk device as outlined Under 21 CFR 812.3(m), as an investigational device that:

1. Is intended as an implant and presents a potential for serious risk to the health, safety, or welfare of a subject

Response: The shock device is not an implantable device.

2. Is purported or represented to be for a use in supporting or sustaining human life and presents a potential for serious risk to the health, safety, or welfare of a subject

Response: The shock device is not for use in supporting or sustaining human life. It does not present a potential for serious risk to the health, safety, or welfare of participants when used as described in this protocol.

3. Is for a use of substantial importance in diagnosing, curing, mitigating, or treating disease, or otherwise preventing impairment of human health and presents a potential for serious risk to the health, safety, or welfare of a subject

Response: The shock device, as used under this protocol is not of substantial importance in diagnosing, curing, mitigating, or treating disease, or otherwise preventing impairment of human health and does not present a potential for serious risk to the health, safety or welfare of a subject.

4. Otherwise presents a potential for serious risk to the health, safety or welfare of a subject

Response: The shock device has been in use numerous for decades and have been cleared by the FDA. Safety guidelines have been developed and updated allowing its dissemination to a wide range of clinical and non-clinical settings. The FDA has generally waived pre-IDE inquiries for shock studies on an NSR device basis. Hence, the CNS IRB, like most US IRBs, has accepted NSR designation for shock device within these limitations.

c. Psychophysiological Recording. The psychophysiological measures that will be obtained are non-invasive, requiring the administration of no needles, drug, or dyes. During electrode placement, the possibility of skin irritation from contact with the saline electrode paste exists. However, this is unlikely since the salt concentration of the paste is similar to that of human sweat. The risk is equivalent to that of an EEG recording. Because the PI’s past studies in anxiety patients and controls using virtually identical recording procedures have resulted in little discomfort to participants, no adverse reactions to such procedures are expected.

d. Auditory Startle Stimulus. Loud sounds can cause hearing problems, but the auditory stimuli that will be used in the startle studies are safe (i.e., there is no danger of hearing impairment). This is because of the physical characteristics of the startle sound (40-ms duration, 102-dB white noise) are within the safe range. Auditory startling sounds of much higher intensities and longer duration (500 ms) are frequently used in startle studies (Hawk & Cook, 2000; Lipp & Siddle, 1998)(Hawk & Cook, 2000; Lipp & Siddle, 1998). Forty-ms/102dB sounds are well below the recommended limits stated in the documentation of various safety regulations. For example, the Occupational Safety & Health Administration (OSHA) recommends that exposure to impulsive or impact noise should not exceed 140 dB peak SPL. The National Institute on deafness and other Communication disorders (NIDCD) website recommends no more than 15 min unprotected exposure at 100 dB. Finally, we use white noise, which are safer than pure tones.

e. Air Puff. The air puff is very intense and mildly unpleasant, but harmless. There is no known risk event associated with the air-puff

f. Experimental Procedures. A series of procedures designed to minimize risk will be applied to participants in this protocol. Both patients and healthy controls will undergo a sample shock procedure before any experiments involving electric shock are run to assess each individual’s reaction to the shock, to adjust the shock to a level that is well tolerated, and to give the participant a chance to withdraw from the study if they so wish. An additional procedure is the observation of participants by way of a non-recording video camera and two-way audio telecom throughout testing. Participants are instructed to signal the experimenter through the video camera or by calling the experimenter’s name at any point during the experiment if they wish to end the experiment or if they wish to speak with the experimenter for any reason. Upon completion of testing procedures for a given visit, patients with a psychiatric disorder are evaluated by [name] to assess for any adverse reactions to experimental procedures. Hence, any problems that stem from these procedures will also be detected and treated in a timely manner.

g. Delayed Treatment. Although anxiety and mood patients will not be taken off any medication for the purposes of this study, we will only include those patients who are not

currently taking psychotropic medications. The only exception to this is the bipolar depressed patients. These individuals, because of the risks associated with mood destabilization, will be permitted to continue taking either Depakote or lithium carbonate as mood stabilizers. Nonetheless, patients included in this study may be at risk of symptom worsening because of the absence of other psychopharmacologic treatment. If patients choose to enroll in the study despite this risk, their symptoms will be monitored by medical staff. If symptoms worsen and are deemed by our medical staff to be a threat to the patient's welfare, the patient will be discontinued from the study and receive brief treatment by our medical staff while referral efforts to community care are underway.

- h. Emotional Pictures.** The emotional pictures will be selected from a set of standardized stimuli that are frequently used in psychophysiological and brain imaging studies of emotions (Lang et al. 1988). Because the intensity of these pictures might make some people uncomfortable, their contents will be fully described to the subjects before participation in the study. The participants will be reminded that they may stop looking at the pictures at any time.
- i. Grip force measures:** This measure is not expected to increase risks in human subjects.

